II. Introduction

Background

Rapid scale-up of antiretroviral therapy (ART) for HIV-infected children and adolescents is anticipated in the near future in response to UNAIDS 90-90-90 fast-track global HIV targets. As more children and adolescents with HIV infection receive first-line ART and many subsequently face the challenge of the treatment failure, the need for second- and third-line ART will also increase.^{i,ii} Barriers to adherence, poor retention in care, gaps in available data and research, as well as limited second- and third-line options for children and adolescents highlight the need to address the issue of treatment failure in these vulnerable sub-groups.^{iii,iv,v,vi,vii,viii,ix} The 2015 World Health Organization (WHO) consolidated treatment guidelines recommend that national HIV/AIDS programs develop third-line ART guidance specifying regimens that include antiretroviral drugs (ARVs) unlikely to have cross-resistance with currently recommended first- and second-line ART regimens, such as integrase inhibitors, second-generation non-nucleoside reverse transcriptase inhibitors (NNRTI) and protease inhibitors (PI).^x Limited data from randomized clinical trials, mainly conducted in high and middle-income countries and among adult populations, demonstrate that etravirine (ETR), darunavir boosted with ritonavir (DRV/r), and raltegravir (RAL) used alone or in combination with other ARVs are efficacious when used in treatment-experienced patients with an optimized backbone. For example, twice daily DRV/r plus an optimized nucleoside/nucleotide reverse transcriptase inhibitor (NRTI) backbone was shown to be virologically and immunologically superior to the control regimen consisting of an investigator-selected control PI plus an optimized backbone in treatment-experienced adults with HIV as shown by a pooled subgroup analysis.^{xi} In treatment-experienced adults with viremia and NNRTI and PI resistance, ETR paired with a background regimen of DRV/r and optimized backbone had improved durable rates of viral suppression and CD4 increase at 96 weeks compared to a similar regimen with ETV-placebo.^{xii} Finally, in patients with multiple drug mutations with limited options for treatment, combination therapy including DRV/r, ETR, and RAL has been associated with high rates of virological suppression at 48-96 weeks.^{xiii,xiv}

Programmatic Response

Janssen (the Pharmaceutical Companies of Johnson & Johnson), the Elizabeth Glaser Pediatric AIDS Foundation (EGPAF), the Partnership for Supply Chain Management (PFSCM), the Collaborative Initiative for Pediatric HIV Education and Research (CIPHER) of the International AIDS Society (IAS), Right to Care, and The Relevance Network have partnered to implement the *New Horizons Advancing Pediatric HIV Care Collaborative* (New Horizons Collaborative) to improve and scale-up pediatric HIV/AIDS care and treatment through increased awareness, research, health systems strengthening, and improved access to HIV/AIDS medicines.

There are various ways that Ministries of Health (MOH) can access DRV and/or ETR, such as through the Global Fund to Fight AIDS, Tuberculosis, and Malaria or other global donors, as well as direct purchase from the manufacturer. However, a primary source of DRV and ETR for pediatric populations in sub-Saharan Africa is through the New Horizons DRV/ETR *Donation Program*. Under the New Horizons Collaborative, a DRV/ETR Donation Program was launched in 2014 to increase access to pediatric HIV medicines for children experiencing ART failure. Under this program, Janssen provides DRV (PREZISTA®) and/or ETR (INTELENCE®) free of charge to eligible national HIV/AIDS programs in sub-Saharan Africa, for use in children and adolescents up to 25 years of age. Upon turning 25 years (or before as required by the national HIV/AIDS program), patients using donated products will be transitioned into the countries' HIV treatment programs for adults as designated by the national HIV program. Under this Donation Program, DRV in combination with ritonavir (RTV) may be used for either second- or third-line treatment after failure on lopinavir/ritonavir (LPV/r) and/or in individuals with virus that has multiple PI resistance mutations. Of note, the Donation Program does not endorse the use of DRV (along with RTV) as second- or third-line therapy for patients who have previously received only NNRTI-based ART regimens (e.g., 2 NRTIs plus nevirapine or efavirenz).

In order to be eligible for participation in the New Horizons Collaborative, countries must satisfy the following criteria:

1. Applicant country must be located in sub-Saharan Africa or else considered to be a Least Developed Country as defined by the United Nations
2. Medicine donation is legal in the applicant country
3. Adult second - and third-line HIV treatment is part of the national HIV program (or will be put in place within 6 months of the applicant country's acceptance into the donation program)
4. The applicant country has national guidelines for second- and third-line pediatric HIV treatment
5. DRV is approved for use in children in the applicant country
6. ETR is approved for use in children in the applicant country
7. There is demonstrated need for second – and third-line ARVs for children, adolescents, and young people
8. The applicant country has necessary clinical expertise to identify children experiencing HIV treatment failure and manage children on second- and third-line treatment
9. Other ARVs, including RTV, needed to create an active regimen with DRV and/or ETR, are available in country

Countries currently participating in the New Horizons Collaborative include:

- Cameroon

- Eswatini
- Ethiopia
- Kenya
- Lesotho
- Nigeria
- Rwanda
- Uganda
- Zambia
- Zimbabwe

Any country that applies and is approved for receipt of donated product will become eligible for this study when they begin offering donated product to patients.

Following acceptance of eligible countries into the New Horizons Donation Program, Janssen and PFSCM have worked with the Ministries of Health (MOH) to forecast and order needed product. Orders of DRV and ETR are shipped to a central warehouse in South Africa, managed by Imperial Health Sciences. Following receipt and processing into South Africa, individual country orders are then sent to the respective MOH.

EGPAF has been provided with funding by Johnson & Johnson Services to manage the country application process and convene the third-party review committee for country selection. EGPAF is also responsible for provision of technical assistance (TA) to national HIV/AIDS programs engaged in the New Horizons Collaborative. In 2014, EGPAF volunteered to conduct a collection of baseline demographic and clinical data for patients receiving DRV and/or ETR through in New Horizons Collaborative countries. The evaluation included 48 patients (45.8% female; median age=15 years) from nine clinical sites in Zambia, Swaziland, Kenya and Lesotho.^{vi} Most children (87.5%) had received ≥ 2 prior ART regimens; 81.2% had received lopinavir/ritonavir-based ART prior to switch. ARV drug resistance was common; of 47 patients with genotype results, 87.2% had ≥ 1 NRTI-resistance mutation (RM), predominantly M184V; 65.9% had ≥ 1 non-NRTI-RM, including 57.4% with ≥ 1 ETR-RM; 63.8% had ≥ 3 protease inhibitor RM, including 42.6% with ≥ 1 DRV-RM. For new ART regimens, DRV and RAL were most frequently prescribed (83.3%; n=40 on DRV and raltegravir, each). Eighteen patients (37.5%) were initiated on the NRTI-sparing ART.^{vi} These data reflect baseline information on children receiving DRV and/or ETR through New Horizons but did not capture new ART regimen treatment response. Hence, EGPAF is proposing to conduct a similar data collection from children and adolescents receiving DRV and/or ETR. For each patient, we will collect demographic, clinical and laboratory data (1) as recorded at the time of initiation on DRV and/or ETR, and (2) updated information approximately every six months, through 2021. New patients will be added to the dataset who have been enrolled since the previous data collection point.

Prior to the inception of the New Horizons Collaborative, no multi-country data were collected regarding the demographic or clinical characteristics of the target patient population (i.e., children, adolescents, and young people < 25 years in need of second- or third-line HIV/AIDS treatment). Therefore, the current activity proposes to collect cross-sectional demographic and clinical data at baseline and every six months for patients receiving DRV and/or ETR across participating New Horizons countries. This activity will comprise data abstraction of a key demographic, clinical, laboratory and case history indicators and outcomes on each patient who ever received DRV and/or ETR.

Objectives

The objectives of this data collection activity are to:

- a) Describe the baseline demographics, clinical and laboratory profile of patients who ever received DRV and/or ETR, at the time of initiation on DRV and/or ETR,
- b) Describe the clinical and laboratory profile of patients who ever received DRV and/or ETR every 6 months from the first data collection point through 2021,
- c) Describe dynamics in HIV drug resistance mutations among patients who fail treatment on new regimens, including DRV and/or ETR.
- d) Describe demographics, clinical and laboratory profile of young adults who transition out of the donation program after the age of 25 years at 12 months after their transition.

Use of Results of this Evaluation

The de-identified data from each participating country will be analyzed and reported to relevant MOH. These overall demographic and clinical findings will be used to describe the children and adolescents who have received DRV and/or ETR up through each time point of data collection. Data from this evaluation will be used as resource when countries review their national guidelines for second- and third-line ART.

The findings will be presented at regional and international scientific meetings or conferences.

Data summarized across New Horizons countries will be shared with programmatic stakeholders and potential New Horizons partners. These stakeholders include the Centers for Disease Control and Prevention (CDC), the United States Agency for International Development (USAID), the United States Office of the Global AIDS Coordinator (OGAC), IAS CIPHER, the Clinton Health Access Initiative (CHAI), PFSCM, various industry partners such as Janssen and Merck, and others.

III. Procedures and Methods

Targeted Facilities

Data collection will occur in the existing clinical programs that are currently managing patients on ART regimens, which include at least one product (i.e., DRV and/or ETR).

Sources of Data

Data will be abstracted from individual patient files/cards stored at the health facility. Only those patient files which represent recipients of DRV and/or ETR will be accessed for the purposes of this activity. All data collection tools and processes will be approved by the in-country IRB. Each patient will be assigned a unique Study identification (ID) number and data collection forms will be linked to the patient using this unique identifier only. The data abstraction team will maintain a master document (“link log”) that allows linking of files of participants to the unique ID. Access to this document will be limited to members of the abstracting team and the evaluation team.

Methods and Timeline

The current data collection activity is intended to describe the demographic, clinical and laboratory characteristics of patients at the point of initiation on DRV and/or ETR and b) the most recently recorded data at the time of most recent data collection point (every six months). Patients will be stratified by the duration of time on ETR and/or DRV.

Members of the abstraction team will visit each participating facility which is handling patients who ever used DRV and/or ETR on a convenient and mutually agreeable day. Because the volumes of patients on DRV and/or ETR are anticipated to be low, data collection activities at each facility are not anticipated to take more than a few hours on a single day. Data abstraction from each patient is expected to be repeated approximately every six months from the last data collection point. The last data collection activity is anticipated to occur in December 2021.

Key Variables

Table 1: Key variables and data source.

Objectives	Variables	Data sources	Comment
a) Describe the demographics, clinical and laboratory profiles of patients who ever received DRV and/or ETR, at the time of initiation on DRV and/or ETR.	
- Age- Gender- Weight- Height (when available)	
- Clinical card- ART register- Lab register	Data collection team should use ART and Lab registers, among others, to complement data not found in the clinical cards

	
 - Viral load at the time of DRV and/or ETR initiation - Baseline ARV drug resistance mutations 		
b) Describe clinical and laboratory profile of patients who ever received DRV and/or ETR every 6 months from the first data collection point through 2021.	
 - Weight - Height - Most recent viral load - Any new genotypic resistance assay results 	
 - Clinical records - ART registers - Lab registers 	Data collection team should abstract data from ART clinical file and ART and lab registers, among other registers. These data will be disaggregated by time duration from last visit as 6, 12, 18, 24, 30 and 36 months.
c) Describe dynamics in HIV drug resistance mutations among patients who fail treatment on new regimens, including DRV and/or ETR.	
 - Weight - Height - Viral load - Duration receiving DRV/ETR - Genotypic resistance test results - Lab based suggested regimen by clinical virologist 	
 - Clinical records - Lab registers 	These data will be abstracted from Laboratory form/register, among other registers.
d) Describe demographics, clinical and laboratory profile of young adults who transition out of the donation program after the age of 25 years at 12 months after their transition.	
 - Weight - Height - Most recent viral load - Any new genotypic resistance assay results 	
 - Clinical records - ART registers - Lab registers 	Data collection team should abstract data from ART clinical file and ART and lab registers, among other registers.

Table 2. Schedule of Evaluation data extraction from each clinical file

Study Activity	Baseline	6 months	12 months	18 months	24 months	30 months	36 months
Demographics	X						
Review Patient Clinical file	X	X	X	X	X	X	X
Record of co-morbidities, such as TB, etc.	X	X	X	X	X	X	X
Weight	X	X	X	X	X	X	X

Height (if available)	X	X	X	X	X	X	X
Results of Viral Load	X ¹	X	X	X	X	X	X
Recorded Clinical diagnosis of Treatment Failure	X	X	X	X	X	X	X
Genotypic Resistance mutation	X	X	X	X	X	X	X
Records of pregnancy	X	X	X	X	X	X	X

Data Handling and Analysis

EGPAF will fund the data collection, data entry, analyses and reporting activities. Data will be abstracted from patient files, ART register or laboratory registers at participating facilities by an EGPAF staff member specifically trained in the objectives and methods of the current assessment (the “abstraction team”). All evaluation team members will be trained in patient confidentiality and human subject protection. Data abstraction will occur in a private location of the health facility to minimize any risk of unauthorized viewing of medical records.

Routinely collected patient-level data will be abstracted from patient files and recorded into a password protected database. Each patient will be assigned a unique study ID and data collection will be linked to the patient using this unique ID only. A master document, “link log” that permits linking of the patient’s name to the unique identification number will be maintained in password protected files by the abstracting team, with access to this document limited to members of the abstracting team and the evaluation team only. Baseline demographic, clinical and laboratory data will be summarized using frequencies and percentages for categorical variables and mean (SD) or median (IQR) for continuous variables depending on their distributions.

Clinical and laboratory follow-up data will be summarized using appropriate descriptive statistics stratified by duration on DRV/ETR. In addition, patient records will be stratified by duration of time on DRV/ETR, and retention on DRV/ETR regimen will be described.

Other analyses may also be conducted using the de-identified data.

Ethical Considerations

Institutional Review Board and Informed Consent

This protocol will be reviewed by an Institutional Review Board (IRB) in the US and an ethical review committee in each of the project countries. The local in-country ethics committees will also receive and approve country-specific details about the evaluation.

This protocol will be conducted with human subject oversight locally in countries participating in the New Horizons Collaborative from the local Institutional Review Boards (IRBs) and in the United States from Advarra IRB (IORG0000635) (Formerly called “Chesapeake IRB”). We are requesting a waiver of consent to abstract data from routine clinic registers, forms, and charts for several reasons, all of which conform with United States (US) Federal regulations OHRP-45CFR46.116, DHHS- 45CFR46.117(c), and HIPAA-CFR 164.512(i)(2)(ii). According to US federal regulations, a waiver of consent is acceptable if the following criteria are met:

- a) The research involves no more than minimal risk to the participants, and involves no procedures for which written consent is normally required outside of the evaluation/research context.
- b) The waiver will not adversely affect the rights and welfare of the participants.
- c) The research could not practicably be carried out without the waiver.
- d) Whenever appropriate, the participants are provided with additional pertinent information after participation.

This evaluation and all the procedures involved with collecting and analyzing routinely program data impose minimal risk to participants because it does not involve direct interaction between the program evaluation staff and patients on DRV and/or ETV. Study numbers will be used and protocols put in place to protect patient identifiers from improper use and disclosure and reduce accidental disclosures. Patient identifiers will be redacted or destroyed at the completion of the study.

A waiver of consent would not adversely affect the rights and welfare of participants because no identifiable information will be recorded in the electronic database. Patient identifiers will only be recorded on an evaluation enrollment log during the data abstraction phase to link patient-level data across routine clinic registers, and clinical cards. When the data abstraction and data cleaning phases have been completed and patient identifiers are no longer required for research purposes, the enrollment log will be shredded. Because age and sex are important variables potentially associated with some of the outcomes to be measured, information on these two variables will be collected. All evaluation staff will be required to sign a confidentiality agreement prohibiting disclosure of any individual-level information including HIV status. The evaluation databases will be password-protected, and all electronic communications involving program evaluation data will be encrypted.

Risks

This study involves minimal risk to participants. All data collected are being abstracted from routinely-collected information in existing medical charts and no interactions

between patients and study staff are required. Key risks involve breaches of confidentiality but steps will be taken to ensure confidentiality and protect privacy.

Confidentiality/Privacy Protections

All evaluation staff members who collect identifiable patient level data or analyze collected data will complete training in human subjects' protections process prior to starting the study.

Standard operating procedures for data security and confidentiality will be implemented and staff will be trained on this protocol. In addition, during site visits, facility staff or MOH representatives may escort data collectors through the facilities, as appropriate. Any breaches of confidentiality will be immediately reported to the EGPAF regulatory officer and appropriate ethical committees, as required.

IV. References

- I. Clavel F, Hance AJ. HIV drug resistance. *N Engl J Med*. 2004;350:1023–35.
- II. Petersen ML, van der Laan MJ, Napravnik S, Eron JJ, Moore RD, Deeks SG. Long-term consequences of the delay between virologic failure of highly active antiretroviral therapy and regimen modification. *AIDS*. 2008;22:2097–106.

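### Follow-up data are put on two conflicting time axes, and no stated rule ties the date of the latest viral load to its time-on-drug label or to 12 months after transition

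*Combined protocol and SAP*

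**What the plan says.** **Which value is taken.** Methods and Timeline defines follow-up as "the most recently recorded data at the time of most recent data collection point (every six months"). Table 1 lists "Most recent viral load" as the viral load variable for objective (b), six-monthly follow-up, and for objective (d), young adults 12 months after leaving the donation program.

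**How it is summarised.** Data Handling and Analysis states: "Clinical and laboratory follow-up data will be summarized using appropriate descriptive statistics stratified by duration on DRV/ETR". Methods and Timeline also stratifies patients by time on the drugs. The comment in Table 1, row (b), gives a different rule: "These data will be disaggregated by time duration from last visit as 6, 12, 18, 24, 30 and 36 months".

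**Text that bears on intent.** Programmatic Response promises "updated information approximately every six months, through 2021" and calls the data cross-sectional: "the current activity proposes to collect cross-sectional demographic and clinical data at baseline and every six months". Table 1, row (a), makes viral load at initiation a variable of its own. Table 2 schedules "Results of Viral Load" at baseline and at 6 to 36 months. It does not say what the months are counted from, and it has no post-transition column.

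**The concern.** A summary by time on drug is readable only if the measurement was taken near the time on its label. Here the value is chosen by one criterion (latest on file at abstraction) and labelled by another (duration on drug), and Table 1 offers a second, incompatible label. Two analysts following different sections would build different strata from the same records.

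Programmatic Response gives the absence of data on response to the new regimens as the reason for this collection, and Objectives offers the results to countries reviewing their second- and third-line guidance. Viral load is one of only two laboratory variables listed for follow-up in Table 1, rows (b) and (d); the other is new genotypic results. A reader of the report could not tell whether a viral load shown at 12 months was drawn near 12 months on drug.

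**Working it through.** The plan states no figure for this point, so there is none to reproduce. The check compares the sections and uses only their dates and intervals.

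**1. The two axes.** Inputs: rounds about six months apart and a last round in December 2021 (Methods and Timeline); labels of 6, 12, 18, 24, 30 and 36 months (Table 1, row (b)). Take a patient abstracted at initiation and every six months after that, with no round missed. Time on drug at round k is 6 × k months. Time since the previous abstraction is 6k − 6(k − 1) = 6 months, whatever k is. The last column follows one viral load drawn at month 6 and not repeated; its age at round k is 6k − 6.

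| Round k | Months on drug | Months since previous abstraction | Age in months of a viral load drawn at month 6 |
|---|---|---|---|
| 1 | 6 | 6 | 0 |
| 2 | 12 | 6 | 6 |
| 3 | 18 | 6 | 12 |
| 4 | 24 | 6 | 18 |
| 5 | 30 | 6 | 24 |
| 6 | 36 | 6 | 30 |

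If the last visit means the last abstraction, labels 12 to 36 are reached only when rounds are missed. If it means a clinic visit, the interval measures the gap in attendance. Neither is duration on DRV/ETR.

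**2. Value and label.** The last column shows what the latest-value rule permits. The month-6 result remains the most recent on file until another test is recorded, so it can be reported under 12, 18 or later months on drug. The table shows that this can happen, not how often. Table 1 asks for any new genotypic result but only the most recent viral load, so its wording does not require a new sample at each round. No supplied section lists a sample date, sets a maximum sample age, or says whether duration is measured at sampling or at abstraction.

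**3. Objective (d).** The objective fixes the time of the profile at 12 months after transition. Its Table 1 row uses the same latest viral load. A patient with no test in those 12 months would contribute a pre-transition sample.

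**4. The upper end.** December 2021 minus 36 months is December 2018. On an initiation axis, anyone who started before then and is still on drug at the last round is past the last label. This shows only that a grouping rule is needed. It does not size the problem of old results.

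**The case against.** The strongest reply is that the intent is clear. Baseline viral load has its own variable and its own Table 2 column, later data are described as updated, and duration on drug is stated in two sections, so the last-visit phrase looks like a wording slip. As a cross-sectional snapshot, the latest value is coherent. The study is descriptive, tests no hypothesis, and records diagnosed treatment failure at every scheduled time in Table 2, so failure is not hidden. Table 1 lists only key variables, and the forms may already capture sample dates. With few patients per facility, a window will thin the strata.

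Most of this stands, and it limits the point. But intent is not a rule: a slip in the analysis text still has to be corrected, and recorded dates do not help unless the plan says how to use them. The snapshot stops being coherent once it is labelled by time on drug.

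Three stronger readings are tempting, and the documents do not support them:

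- **A third analysis axis.** Objective (b) speaks of "every 6 months from the first data collection point through 2021". That sets when rounds take place, not how results are labelled.
- **Baseline values reported as follow-up.** A reader might infer that pre-initiation results will be counted as response. The separate baseline variable and the promise of updated information make that strained.
- **Objective (d) has no time point.** It does, at 12 months after transition. What is missing is a tie between that point and the sample.

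**Conclusion.** The point holds in two parts. The analysis text contains two incompatible time axes; this follows from the wording and the six-monthly interval alone. Separately, the plan as supplied has no rule linking the viral load sample date to its time-on-drug stratum or to a window around 12 months after transition, so an old result can be reported under a later label.

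The share of results affected is unknown. It depends on how often viral load is tested, which the documents do not give, so no percentage is offered. The second part also rests on incomplete material: the data collection forms were not available, nor was the text of the footnote on the baseline viral load cell of Table 2, although that footnote is attached to the baseline cell only. The finding is that the rule is unstated, not that dates will go uncollected.

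The effect is on how the time-stratified summaries can be read; no error rate or power is involved. The plan should be changed, because response to the new regimens is its stated purpose and the correction is small.

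**What to change.** - In Table 1, row (b), replace time since the last visit with time from DRV/ETR initiation to sample date. Use the same axis in Methods and Timeline and in Data Handling and Analysis. Because the population is everyone who ever received either drug, note that this equals time on drug only while the patient remains on it.
- Abstract the sample date with each viral load, if the forms do not already record it.
- In summaries by time on drug, use only post-initiation samples within a pre-stated window chosen by the sponsor, and show the number of patients with no result in each stratum.
- State how results past 36 months on drug are grouped.
- For objective (d), use a post-transition sample in a stated window around 12 months.
- A latest-value snapshot may still be reported if it is labelled as one.

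The cost is about one paragraph of analysis text and slightly more abstraction work; if the forms already hold sample dates, only the text changes. The drawback is that more values will be shown as missing.

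### The latest-value rule for follow-up viral load leaves earlier results unabstracted in patients already on DRV/ETR, and the plan's three time origins are not reconciled

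*Combined protocol and SAP*

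**What the plan says.** The last paragraph of Programmatic Response sets the population: data are abstracted "on each patient who ever received DRV and/or ETR". This includes patients who started before data collection began. The same section says that "a DRV/ETR Donation Program was launched in 2014", and justifies the new collection by noting that the earlier survey of 48 patients "did not capture new ART regimen treatment response".

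Four places then govern follow-up:

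- **Objective (b)** describes patients "every 6 months from the first data collection point through 2021".
- **Methods and Timeline** takes characteristics at initiation, then "the most recently recorded data at the time of most recent data collection point", with rounds about every six months and the last expected in December 2021.
- **Table 1, objective (b)** lists "Most recent viral load", together with weight, height and any new genotype results. Its comment column splits the data into 6 to 36 months counted from the last visit.
- **Table 2** ("Schedule of Evaluation data extraction from each clinical file") has columns from baseline to 36 months, with a viral load row marked in every column. It does not say what the months are counted from.

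The analysis text, under Data Handling and Analysis, reads: "Clinical and laboratory follow-up data will be summarized using appropriate descriptive statistics stratified by duration on DRV/ETR".

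**The concern.** The study exists to fill a gap in response data, and its main reporting axis is time on drug. The collection rule follows a different axis: one viral load per round, starting at the first round. For someone who had been on DRV/ETR for years by then, the literal rule gives a value at initiation and then one late value. Results in between may sit in the file that the abstractor has open, yet nothing clearly tells the abstractor to take them.

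Two consequences follow for viral load. The early-duration strata would be filled mainly by patients who started shortly before or after the first round, so a comparison of early with late strata would partly compare start cohorts. A patient who became viraemic and re-suppressed before the first round, or between two rounds, could appear as continuously suppressed. The Use of Results section says that the data will serve countries reviewing their second- and third-line guidelines, so a distorted picture of early response would matter.

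**Working it through.** The study is descriptive. It states no sample size, power or test, so there is no plan figure to reproduce. The check is calendar arithmetic plus a comparison of passages.

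**Inputs**

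- Earliest program start: 2014 (Programmatic Response). The month is not given, so I range from 1 January to 31 December 2014.
- Last round: December 2021 (Methods and Timeline).
- Last schedule column: 36 months (Table 2). Six-monthly steps give 36 / 6 = 6 follow-up columns.
- First round: not stated. *Assumption:* no earlier than 14 November 2017, the date of the newest cited source (References), since the protocol still describes the work as proposed. I range it to December 2019.

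**Time on drug at the first round**

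Months on drug = (first-round date − initiation date) in days / 30.4375. Example for 14 November 2017: from 1 January 2014, 1413 / 30.4375 = 46.4; from 31 December 2014, 1049 / 30.4375 = 34.5.

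| Assumed first round | 2014 starters: months on drug | Six-month columns already elapsed | Past 36 months on drug if started before | Months from first round to December 2021 |
|---|---|---|---|---|
| 14 Nov 2017 | 34.5 to 46.4 | 5 to 6 | 14 Nov 2014 | 48.6 |
| Jun 2018 | 41.0 to 53.0 | 6 | Jun 2015 | 42.0 |
| Dec 2018 | 47.0 to 59.0 | 6 | Dec 2015 | 36.0 |
| Jun 2019 | 53.0 to 65.0 | 6 | Jun 2016 | 30.0 |
| Dec 2019 | 59.0 to 71.0 | 6 | Dec 2016 | 24.0 |

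Later starters are affected less. A patient who started on 31 December 2016 is 10.4 months on drug at a November 2017 first round and 23.0 months at one in December 2018.

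**Who can fill an early stratum**

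Under the literal rule, a follow-up viral load dated near the first round falls within the first 12 months on drug only if initiation was within 12 months before that round or came later. That means a start from about November 2016 for a November 2017 round, or from December 2017 for a December 2018 round. The latest recorded value can itself be some months old, so the early strata would hold mainly, not exclusively, later starters.

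**The 36-month limit**

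- Counted from initiation: December 2018 to December 2021 is 36 months, so everyone who started before December 2018 passes the last column by the final round. A 2014 starter is then at 84 to 96 months.
- Counted from the first round: the schedule fits if that round is in December 2018 or later (36.0 months or less) and is exceeded if it is earlier (48.6 months from November 2017).

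**Time origins side by side**

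Baseline and the analysis strata use initiation. Objective (b) uses the first data collection point. The Table 1 comment uses the last visit. Table 2 names none. An abstractor following Methods and Timeline and one following Table 2 as a back-abstraction schedule would produce different datasets from the same chart.

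**The case against.** The strongest reply is that Table 2 already provides for the history. It describes extraction from each file and marks viral load in every column, so if its months run from initiation, an abstractor could fill months 6 to 36 from the chart. That reading is possible and stands as a reason not to call the loss certain. It does not settle the matter, because Methods and Timeline and Table 1 say something different and Table 2 gives no origin.

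A second reply is that the protocol declares a cross-sectional collection at baseline and every six months, with objective (b) openly starting at the first round. This also stands: taking all dated results improves the design rather than correcting a mistake. But the stated purpose is treatment response and the analysis runs by time on drug, and the current rule serves both poorly.

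Three stronger readings are tempting, and the documents do not support them:

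- *Genotypes from before the first round are overwritten.* Table 1 asks for any new genotype result under objective (b). For objective (c) it lists genotype results, viral load without a latest-value restriction, and duration on drug. Table 2 also records treatment failure in every column.
- *The same people cannot be followed over time.* Each patient keeps one study ID and is re-abstracted about every six months. From the first round, individual follow-up is intact.
- *Data beyond 36 months are lost.* Collection runs through 2021 and the duration-stratified analysis has no stated cap. What is missing is a column or stratum for those data.

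**Conclusion.** The point holds for viral load. As written, interim viral loads between initiation and the first round, and all but the latest between rounds, are not clearly abstracted, and the time origins are unreconciled. The exposure is greatest for the earliest starters: 34.5 to 46.4 months of treatment before a first round in November 2017, and more for any later round.

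These month counts rest on an assumed first-round date. The number or share of patients affected cannot be derived, because the documents give no distribution of initiation dates (including for the 48 earlier patients) and no viral load testing frequency. The abstraction form is not in the documents, so it may already capture dated results. The 36-month shortfall is conditional: it arises if months count from initiation, or if they count from a first round before December 2018. This is a worthwhile, inexpensive improvement and does not invalidate the study.

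**What to change.** 1. Name DRV/ETR initiation as the single time origin in Objective (b), Table 1 and Table 2, and replace the last-visit wording in Table 1. Rounds can stay six-monthly by calendar; only the reporting axis needs to be fixed.
2. At each patient's first abstraction, take every dated viral load since initiation, with dated weight, height and recorded treatment failure. At later rounds, take every dated result since the previous round. Amend Methods and Timeline and Table 1 to say so.
3. With months counted from initiation, add duration strata beyond 36 months, in 6- or 12-month steps, up to the longest follow-up possible at December 2021 (84 to 96 months for 2014 starters).

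The cost is a few more lines per chart, in charts already being opened and at volumes that the protocol expects to be low. The abstraction form would need amending. Sources of Data requires in-country ethics approval of collection tools, and ten countries are listed as participating, with a US board as well, so the administrative effort is real though modest. If the form already records all dated results, only the protocol text needs to change.
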